**ClinicalTrials.gov ID#: NCT01550315**

## 1.0 BACKGROUND

### 1.1 Endothelium

The endothelium is the thin layer of cells that lines the interior surface of blood vessels. It functions as an inert barrier between the vascular system and all other body tissues. Additionally, it aids in modulating hemostasis, growth, tone and inflammation throughout the circulatory system. The endothelium maintains the vasculature in a steady dilated state. Endothelial dysfunction has been identified in several pathologic states such as diabetes, hypertension, age, cigarette smoking, obesity and several cardiovascular diseases . The pathophysiology of endothelial dysfunction is not fully understood. Studies have demonstrated impairment in nitric oxide (NO) metabolism of which several mechanisms have been postulated including: abnormally elevated asymmetric dimethylarginine (ADMA) level- a potent endogenous competitive inhibitor of NO , overproduction of free radicals which have been identified in patients with elevated cholesterol and coronary artery disease and reduction in NO synthesis . Impaired availability of NO has been implicated in the development of coronary artery disease, and poorly controlled hypertension .

### 1.2 Dietary Sodium Levels

According to the most recent report by institute of medicine (IOM), most Americans consume an average of sodium in excess of 3400 mg. This far exceeds the center for disease (CDC) recommendation of less than 2300 mg or less than 1500 mg for high risk groups with hypertension, diabetes, African Americans, or chronic kidney disease. The American Heart Association has recently recommended an average dietary sodium intake not exceeding 1500 mg across all age groups .

Dietary sodium have been implicated in endothelial dysfunction, with increasing evidence linking salt intake to increased risk of cardiovascular disease and elevated blood pressure . Excess salt intake in mammalian study has demonstrated increased mortality by accelerating arteriosclerosis and renal parenchyma damage . Strazullo et al. performed a meta-analysis that suggested a significant increased risk of stroke and total cardiovascular events among those with a high salt diet .

### 1.3. Endothelial dysfunction and oral salt diet

Short-term high salt intake has been shown to produce reductions in NO as reported by Dishy et al. . Elevated ADMA was also implicated in patients with high salt diet by a study reported by Fujiwara et al. . Many of these studies have assessed patients on their native diets, and thus may be confounded by many unknown variables. Most of these studies were also carried out on middle aged or older patients with cofounding risk factors such as hypertension. We propose to study young to middle aged subjects who will undergo acute, but steady state HIGH and LOW sodium diets, and assess the acute changes in measures of endothelial events. Differences in measures of endothelial function between the diet phases might suggest that dietary sodium intake is an important variable that would need to be controlled in future studies of endothelial function.

## 2.0 REACTIVE HYPEREMIA PULSITLE ARTERIAL TONOMETRY (RH-PAT)

### 2.1 RH-PAT Device

The principle of PAT, a finger plethysmographic device that allows the isolated detection of pulsatile arterial volume changes, has been described. This device (Itamar Medical Ltd., Caesarea, Israel) consists of two finger-mounted probes, which include a system of inflatable latex air-cushions within a rigid external case. The probe design allows the application of a constant and evenly distributed near-diastolic counter-pressure within the entire probe, which increases sensitivity by unloading arterial wall tension, and prevents venous blood pooling to avoid venoarteriolar reflex vasoconstriction. Pulsatile volume changes of the fingertip are sensed by a pressure transducer and transferred to a personal computer where the signal is band pass-filtered (0.3 to 30 Hz), amplified, displayed, and stored.

## 2.2 RH-PAT and Other Methods for Assessing Vascular Endothelial Function in Vivo

Reactive hyperemia, which is due to dilation of small resistance vessels, is partly mediated by endothelium-derived NO and, therefore, the magnitude of the hyperemic response

[figure not shown]

Figure 5: RH-PAT responses before and after brachial artery occlusion.

serves as an indicator for the status of endothelial function. Moreover, using strain-gauge plethysmography, an excellent correlation between peak forearm blood flow response during RH and that to intra-arterial infusion of the endothelium-dependent vasodilator

acetylcholine has been demonstrated, indicating that the magnitude of RH may serve as an index of peripheral endothelial function; RH-PAT permits the noninvasive assessment of peripheral vascular reactivity by measuring digital pulse volume at rest and during RH. Notably, although local, systemic, and environmental factors may modulate digital pulse volume, this parameter also depends on the bioavailability of NO. Moreover, endothelium-derived NO has been shown to be particularly important for the regulation of vascular tone in areas rich in arteriovenous anastomoses, such as the finger tip. The effect of NO synthesis inhibition by Nω-nitro-**L**-arginine methyl ester (**L**-NAME) on the PAT response to reactive hyperemia was investigated recently. In that study, 19 healthy volunteers underwent RH-PAT testing, according to the same protocol as was used in the present study, before and after administration of **L**-NAME into the brachial artery. Importantly, **L**-NAME administration was associated with a significant 61% reduction ( $p < 0.05$ ) in the RH-PAT index values, indicating that this index depends on endothelium-derived NO and, therefore, represents a marker of peripheral

endothelial function. In accordance with these findings, it was demonstrated that factors known to affect endothelial function, including various cardiovascular risk factors and the presence of CAD, influence RH-PAT index values in a similar manner as flow-mediated dilation (FMD) of the brachial artery, a widely-used method to evaluate peripheral endothelial function . Furthermore, a significant relationship between the PAT response to reactive hyperemia and flow-mediated dilation of the brachial artery has been shown, suggesting that vascular reactivity of the digital vasculature, as measured by the RH-PAT index, is influenced by endothelial function in a magnitude and direction similar to that of the brachial artery .

Vasodilatation of a peripheral conduit artery following an increase in luminal blood flow and internal-wall shear is known as flow-mediated dilatation (FMD). In practice it is performed following a period of distant limb ischemia. Strong evidence suggests that FMD is a valid endothelium-dependent and NO-specific index of endothelial function. To measure FMD we will adhere to current guidelines .

### 3.0 EX-VIVO ASSESSMENT OF ENDOTHELIAL FUNCTION

The endothelium can no longer be viewed as the passive inner cover of the vessel wall. It plays a central role in cardiovascular regulation. Endothelial cells produce a variety of vasoactive substances that can act locally or at distant sites. Among these substances nitric oxide (NO) is probably the most heavily studied, and its reduced bioavailability is widely accepted to be responsible for endothelial dysfunction. Reduction of NO bioavailability can result from a defective eNOS expression/activity or from an excessive NO degradation, usually through an interaction with superoxide ( $O_2^-$ ) that generates peroxy nitrites (ONOO $^-$ ). Endothelial damage is the first step of vascular remodeling. Unfortunately, the endothelium has a limited ability to repair itself and hence prevent or reverse endothelial dysfunction. In animal models, direct information on the anatomical and function integrity of the endothelium can be easily obtained. In humans, endothelial function is usually assessed indirectly as the NO-dependent vasodilatory capacity of a given vascular bed to an endothelial stimulus either mechanical (shear stress, reactive hyperemia) or pharmacological (NO-dependent vasodilators, NOS inhibitors). This indirect approach is however subjected to intra-patient variability, confounding effects, and cannot distinguish between anatomical and functional alterations. Other clinical indicators of endothelial dysfunction are represented by circulating substances such as VCAM-1, ICAM, vWF, ADMA, and thrombomodulin, indicating pathological activation of the endothelium in the setting of a low grade inflammatory state. Relatively recently, more direct *ex vivo* approaches have been developed to study the human endothelium, these include the study of mature circulating endothelial cells that may detach at an increase rate due to ongoing endothelial damage and can be isolated and incubated. Similarly, circulating endothelial progenitor cells, discovered in 1997, can be obtained and cultivated to study mechanisms of vascular repair and regeneration. A third method involves the harvesting of viable endothelial cells via an endothelial biopsy, this allow the study of gene and/or protein expression.

Endothelial biopsy has been used to quantify eNOS expression (by measuring the protein expression of eNOS), its activity [by measuring Ser-1177 phosphorylated eNOS (P-eNOS)] and also NO-dependent reactive oxygen induced stress (by measuring nitrotyrosine). Ideally samples from a suspected damaged artery (coronary) should be obtained, either during routine cardiac catheterization or after the procedure has been performed, however this is not always possible to

do. Vein sampling has the advantage of its accessibility and it has reported a good correlation ( $r=0.7$ ) for protein expression of eNOS, P-eNOS and nitrotyrosine from samples obtained from a peripheral artery and the brachial artery.

## 4.0 HYPOTHESIS & SPECIFIC AIMS

### 4.1 Hypothesis

In this pilot crossover study, we will test the hypothesis that markers of vascular endothelial dysfunction will be exaggerated acutely with an extreme high-sodium diet compared to an extreme low-sodium diet.

### 4.2 Specific Aims

1. To assess whether RH-PAT (marker of peripheral small vessel endothelium dependent nitric oxide mediated vasodilatation) will be reduced in subjects on a high sodium diet compared with a very low sodium diet.
2. To assess whether brachial artery flow-mediated vasodilatation (marker of endothelium dependent nitric oxide mediated vasodilatation in a conductance vessel) is reduced on extreme high sodium diet compared to a low sodium diet.
3. To assess whether circulating markers of endothelial function will be reduced in subjects on a high sodium diet compared with a very low sodium diet.
4. To assess whether calf blood flow in response to reactive hyperemia (CBF-RH) correlates with RH-PAT.

## 5.0 INCLUSION/EXCLUSION CRITERIA

### 5.1 Inclusion Criteria

- Subjects will be enrolled in the parent study “Dietary Salt in Postural Tachycardia Syndrome” funded by R01 HL102387
- Postural Tachycardia Syndrome
  - Diagnosed with postural tachycardia syndrome by the Vanderbilt Autonomic Dysfunction Center
    - Increase in heart rate  $\geq 30$  beats/min with position change from supine to standing (10 minutes)
    - Chronic symptoms consistent with POTS that are worse when upright and get better with recumbence
- Control Subjects
  - Healthy, non-obese, non-smokers without orthostatic tachycardia
  - Selected to match profiles of POTS patients (gender, age)
  - Not using vasoactive medication
- Age between 18-60 years
- Male and female subjects are eligible.
- Able and willing to provide informed consent

### 5.2 Exclusion Criteria

- Overt cause for postural tachycardia (such as acute dehydration)
- Inability to give, or withdrawal of, informed consent
- pregnant

- Other factors which in the investigator's opinion would prevent the subject from completing the protocol.

## **6.0 ENROLLMENT, RANDOMIZATION & BLINDING**

### **6.1 Recruitment**

For the parent study, the patients with orthostatic intolerance will be recruited from patients referred to the Vanderbilt University Autonomic Dysfunction Center. Control subjects will be recruited from the Autonomic Research Database, the VICTR Research Participant Database, and advertising within the Vanderbilt Community. For this protocol, subjects enrolled in the parent study will be approached about this sub-study. Subjects will be assured that they are not required to participate in this study even if they choose to participate in the parent study.

### **6.2 Randomization**

There will be no randomization for this specific sub-study. The order of diets (low sodium vs. high sodium) will be performed as a part of the parent study, and not as a part of this sub-study.

### **6.3 Blinding**

None.

## **7.0 STUDY PROCEDURE**

### **7.1 Screening**

All subjects will be previously screened and evaluated as a part of the parent study. No further screening will be performed exclusively for this study. Women of childbearing potential will have had a serum pregnancy test as a part of the parent study. Pregnant women will not be allowed to participate.

The history will include (but not be limited to):

- Framingham Risk factors (age, gender, smoking, hypertension, dyslipidemia)
- Metabolic diseases (metabolic syndrome, polycystic ovary syndrome, diabetes)
- Inflammatory diseases (e.g. rheumatoid arthritis).

The physical examination will include (at minimum):

- Height
- Weight
- Waist circumference
- Hip circumference
- Orthostatic vital signs.

### **7.2 Study Design**

The study will involve a crossover design in which each subject will be assessed (as below) while on a very low-sodium (10 mEq/day) diet compared with a very high-sodium diet. These acute dietary interventions will be part of the parent study ("Dietary Salt in Postural Tachycardia Syndrome" funded by R01 HL102387) for 4-5 days at the time of the study.

Dietary success will be assessed using a 24h urine for sodium and creatinine as a part of the parent study.

### 7.2.1 Blood work

Blood will be drawn and collected in a **fasting state** for future assay and analysis of the following tests:

- Glucose, Insulin (glucose impairment, insulin resistance)
- Fasting lipid profile
- C-Reactive Protein (hsCRP) (inflammatory state)
- Inflammatory cytokines (inflammatory state)
- F2-isoprostanes (oxidative stress)
- PAI-1 antigen, fibrinogen (prothrombotic state)

### 7.2.2. Urine Collection

A morning urine sample will be collected, and an aliquot saved for urinary isoprostanes.

### 7.2.3 Pulsatile Arterial Tonometry (PAT) Protocol

- Performed on Day 6 of parent protocol (5 days of low/high sodium diet).
- All studies will be performed in a fasting state or at least 2 hours following a meal.
- Subjects will be studied in the supine position and both hands on the same level in a comfortable, thermoneutral environment.
- A blood pressure cuff will be placed on one upper arm (study arm; non-dominant), while the contralateral arm will serve as a control (control arm).
- RH-PAT probes will be placed on one finger (finger II, III, or IV) of each hand (same finger on both hands). The fingers on either side of the one with the probe will be separated using soft sponge rings.
- Continuous recording of pulsatile blood volume responses from both hands will be initiated.
- After a 10-min equilibration period, the blood pressure cuff on the study arm will be inflated to 60 mm Hg above systolic pressure for 5 min. The cuff will then be deflated to induce reactive hyperemia, PAT recording will be stopped.

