#### **7.2.6 Evaluation of Forearm-Mediated Dilatation**

Subjects will be fasting for at least 2 hours prior to the study and will be instructed to avoid exercising the day before the study. All studies will be conducted in a quiet, temperature-controlled room. All subjects will rest in the supine position for at least 30 minutes after all instrumentation procedures are done. The arm will be kept extended and immobilized at heart level. Brachial artery diameter will be measured using a high resolution ultrasonography (iU22 xMatrix Ultrasound System, Philips, Andover MA) using a linear array probe with a 5 to 17 MHz frequency range (L17-5 Broadband Linear Array Transducer, Philips, Andover MA). The brachial artery will be imaged in longitudinal sections, 5-10 cm proximal to placement of an occlusion cuff in the dominant forearm just below the antecubital fossa. The probe will be held with a stereotaxic holder with micrometer movement capabilities.

When the clearest B-mode image through the center of the vessel is obtained with optimal contrast between the anterior and posterior vessel walls and the lumen of the vessel, the stereotaxic clamp will be fixed in place. Baseline diameter will be examined before cuff inflation for at least 1 minute. The rapid occlusion cuff (Hokanson) will be inflated and maintained for 5 minutes at 50 mm Hg above the subject's systolic blood pressure to produce transient ischemia. Measurement of post-deflation diameter will be initiated before cuff release and continue for 5 minutes following deflation.

Flow velocity and brachial artery diameter will be continuously measured using duplex ultrasound. Blood velocity will be assessed using an insonation angle <60°. The B-mode will

update synchronously with the R-wave of the ECG while also having a continuous Doppler spectrum recording throughout.

One experienced sonographer will collect all images. Images will be digitized from the video output of the ultrasound machine using a frame grabber on a personal computer. Image acquisition will be gated with an ECG signal so that images will be captured at end diastole at each cardiac cycle.

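### RH-PAT may be measured in either of two prandial states and on any of three fingers, and nothing requires a subject's two diet visits to match or either factor to be recorded

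*Combined protocol and SAP*

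**What the plan says.** Section 8.1 makes the RH-PAT index the primary outcome. It is compared between the two diets by a paired signed rank test over all subjects, with no covariates.

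Section 7.2.3 gives the test conditions:

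- **Prandial state:** "All studies will be performed in a fasting state or at least 2 hours following a meal".
- **Probe site:** "RH-PAT probes will be placed on one finger (finger II, III, or IV) of each hand (same finger on both hands"). The bracketed rule pairs the two hands within one session. It does not pair the two diet visits.
- **Timing:** "Performed on Day 6 of parent protocol (5 days of low/high sodium diet").
- **Posture and room:** "Subjects will be studied in the supine position and both hands on the same level in a comfortable, thermoneutral environment".
- **Arm:** "A blood pressure cuff will be placed on one upper arm (study arm; non-dominant), while the contralateral arm will serve as a control".

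Section 7.2.4 has the index computed without operator input, as a ratio to the pre-occlusion baseline, and then normalised to the control arm. Section 7.2.1 requires fasting for the blood draw but does not tie PAT to that draw. For FMD, the section on forearm-mediated dilatation says: "Subjects will be fasting for at least 2 hours prior to the study". Section 1.3 describes the exposure of interest as "acute, but steady state HIGH and LOW sodium diets". Under Sections 6.2 and 7.2, the diets and their order belong to the parent study, whose protocol is not among the documents.

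**The concern.** In a paired analysis each subject is their own control, so stable differences between people cancel. Conditions that change between one person's two visits do not cancel. The meal rule lets the same subject be tested fasting on one diet and some hours after a meal on the other. The finger rule lets the probe sit on different fingers at the two visits.

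Prandial state matters more than usual here because the intervention is food. A test after a study meal may include a response to that recent high- or low-sodium meal as well as the effect of several days on the diet. A fasting test is closer to the steady-state contrast that Section 1.3 describes.

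Two things are at stake. Mismatch unrelated to diet widens the paired difference and costs power. Mismatch related to diet would shift the primary result. Since neither factor has to be recorded, neither problem could be checked or adjusted for afterwards.

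**Working it through.** **Inputs from Section 8.3.** Target difference 0.25; SD of the paired difference 0.5; two-sided alpha 0.05; 44 subjects for 90% power, or 33 for 80%.

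**The plan's own figures.** Paired t-test power from the noncentral t distribution, with noncentrality (0.25/0.5) × √n:

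- n = 44: power 90.0%, as stated.
- n = 33: power 79.5%, which agrees with the stated 80% after rounding.

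The planned test is a signed rank test. Simulation with normal differences gives about 89.5% at 44 and 77.3% at 33, so the t-test is a fair stand-in at the main sample size.

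**Where the SD comes from.** The cited SEM of 0.08 in 39 subjects gives 0.08 × √39 = 0.4996. That is a between-subject SD of single measurements. It makes no explicit allowance for a change of meal state or finger between visits, though it may already contain some variation of that kind.

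**Mismatch unrelated to diet (assumed sizes).** Let a share f of pairs be mismatched, with direction random and independent of the diet effect, and let the mismatch move RH-PAT by s. The mean difference is unchanged and its variance rises by f × s²:

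SD = √(0.5² + f × s²)

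| f | s | SD of difference | Power, n = 44 | Power, n = 33 |
|---|---|---|---|---|
| any | 0 | 0.500 | 90.0% | 79.5% |
| 0.25 | 0.2 | √0.26 = 0.510 | 88.9% | 78.0% |
| 0.50 | 0.2 | √0.27 = 0.520 | 87.7% | 76.4% |
| 0.50 | 0.3 | √0.295 = 0.543 | 84.7% | 72.7% |
| 0.50 | 0.4 | √0.33 = 0.574 | 80.6% | 67.9% |

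**Mismatch that tracks diet (illustration only).** Bias = (net share of pairs mismatched in one direction) × s. With no net imbalance the bias is 0 and type I error stays at 5%. An assumed net imbalance of 30% gives 0.3 × 0.2 = 0.06 to 0.3 × 0.4 = 0.12, which is 24% to 48% of the 0.25 target. With n = 44, SD 0.5 and no true diet effect, t-test type I error would then be about 12% to 34%. The documents support neither the imbalance nor the shift; these figures only show how the result would respond.

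**The case against.** A reader might infer that the diet contrast is in fact mixed with a fed-versus-fasted and finger difference. The documents do not support that. Section 7.2.3 permits variation; it does not show that staff would vary either factor within a subject. Bias would need meal state or finger to follow diet. Both diets are under the same Day 6 rule, and no section links either factor to diet. The absence of blinding (Section 6.3) makes such a link possible, not likely.

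The existing safeguards are real. Day, posture, room, arm, equilibration period and within-session finger are fixed. The index is automated, relative to the subject's own baseline, and normalised to the control arm. The meal rule also sets a common two-hour minimum, so no test may follow immediately after eating. The parent protocol may fix meal timing too, which cannot be checked here.

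The assumed shifts can also be challenged. Section 8.3 gives a healthy mean of 1.78 and a discriminating cut-off of 1.35, a gap of 0.43. A shift of 0.4 would be nearly all of that and more than the 0.25 called clinically significant, so the upper end looks large. Even there, power at 44 stays near 81%, about the level the plan accepts as its fallback. If the SD of 0.5 already includes some of this variation, the table overstates the loss.

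These arguments limit the size of the problem but do not remove it. Control-arm normalisation addresses systemic change. It need not cancel a meal effect on the hyperaemic response itself, because the control arm is not occluded, and it does not make one finger equivalent to another. The fasting blood draw does not govern PAT, which has its own looser rule.

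**Conclusion.** The point stands as an avoidable weakness in how the primary outcome is standardised. The plan does not require, record or adjust for the same prandial state and finger at a subject's two diet visits, and the primary test is an unadjusted paired comparison. The supported consequence is possible extra noise. Under the assumed shift of 0.2 to 0.4 with 25% to 50% of pairs mismatched at random, power at 44 subjects is about 89% to 81% instead of 90%; with no shift there is no loss.

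Bias remains conditional on mismatch that tracks diet, and it should not be reported as a finding. The sample-size calculation reproduces and is not in question. The change is worth making because it costs little and because neither factor could be reconstructed later if left unrecorded.

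**What to change.** In Section 7.2.3:

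1. Require the fasting state at both diet visits, replacing the present either/or rule. Matching two post-meal visits would remove the fed-versus-fasted difference but leave a difference in the sodium content of the recent meal.
2. Require the same finger at both visits for each subject.
3. Record prandial state and finger for every test.

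Apply the same prandial condition to FMD in the section on forearm-mediated dilatation. State once what fasting means, because that section uses the word for a two-hour interval while Section 7.2.3 lists fasting and the two-hour interval as alternatives. If the parent protocol already fixes meal timing on Day 6, a cross-reference may cover the first item.

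The cost is slightly tighter visit scheduling and two recorded items per test. Matching clock time is optional. The sample size and the primary test do not change.

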### 7.2.4 PAT Analysis

The RH-PAT data will be analyzed by a computer in an operator-independent manner. As a measure of the extent of reactive hyperemia, the RH-PAT index was calculated as the ratio of the average amplitude of the PAT signal over a 1-min time interval starting 1 min after cuff deflation divided by the average amplitude of the PAT signal of a 3.5-min time period before cuff inflation (baseline). RH-PAT index values from the study arm were then normalized to the control arm to compensate for potential systemic changes.

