## 8.0 STATISTICAL CONSIDERATIONS

### 8.1 Primary Analysis

The primary outcome measure will be the RH-PAT index. The primary analysis will involve a non-parametric, paired, Signed Rank test of RH-PAT between all subjects (POTS patients and control subjects) on the high sodium diet vs. the low sodium diet.

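### Does Section 7.2.3 stop the PAT recording before the signal needed for the primary RH-PAT index has been captured?

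*Combined protocol and SAP*

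**What the plan says.** Section 7.2.3 lists the steps of the tonometry session. Both hands are recorded from before equilibration: "Continuous recording of pulsatile blood volume responses from both hands will be initiated". The timed steps follow: "After a 10-min equilibration period, the blood pressure cuff on the study arm will be inflated to 60 mm Hg above systolic pressure for 5" minutes. The last sentence is "The cuff will then be deflated to induce reactive hyperemia, PAT recording will be stopped". No recording time after deflation is given there or elsewhere in the document.

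Section 7.2.4 defines the index. The numerator is the mean PAT amplitude "over a 1-min time interval starting 1 min after cuff deflation", and the denominator is the mean amplitude over the 3.5 minutes before inflation. The section adds that "RH-PAT index values from the study arm were then normalized to the control arm".

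Section 2.2 describes the method as "measuring digital pulse volume at rest and during RH". Section 8.1 fixes the role of the index: "The primary outcome measure will be the RH-PAT index".

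**The concern.** Section 7.2.3 is the acquisition procedure, and its last sentence puts deflation and the end of recording side by side. Someone who took it to mean that both happen at once would capture the baseline but nothing of the response. The index could then not be computed, and computerised analysis cannot recover signal that was never recorded.

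The endpoint at stake is the primary one. The primary test is paired across the two diets, so a subject needs a complete numerator at both visits, and one truncated recording removes the pair.

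The contrast with the other two reactive-hyperaemia measurements sharpens the point. The brachial ultrasound procedure says that measurement will "continue for 5 minutes following deflation", and the calf blood flow procedure in Section 7.2.5 gives 3 minutes of measurement. Only the procedure behind the primary outcome states no period.

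**Working it through.** **The plan's own design figure.** Section 8.3 uses a difference of 0.25 and an SD of the difference of 0.5, so the effect size is 0.25 / 0.5 = 0.5. The SD agrees with the cited SEM: 0.08 × √39 = 0.4996. For a paired t-test at two-sided 0.05 (noncentral t), 44 subjects give 90.0% power, which reproduces the plan, and 33 give 79.5%, close to the stated 80%. Recording time is not an input to any of these figures.

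**Timeline.** Let minute 0 be the start of equilibration, with recording already running (Section 7.2.3).

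| Event | Source | Arithmetic | Minute |
|---|---|---|---|
| Cuff inflation | 7.2.3 | 0 + 10 | 10 |
| Cuff deflation | 7.2.3 | 10 + 5 | 15 |
| Baseline window opens | 7.2.4 | 10 − 3.5 | 6.5 |
| Baseline window closes | 7.2.4 | at inflation | 10 |
| Numerator window opens | 7.2.4 | 15 + 1 | 16 |
| Numerator window closes | 7.2.4 | 16 + 1 | 17 |

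The baseline window lies wholly within the 10 minutes of equilibration. The numerator window lies after minute 15, where the stated durations end. The least recording after deflation is 17 − 15 = 2 minutes, on both hands because of the control-arm normalisation.

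**Two readings of the last sentence of Section 7.2.3.**

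1. Recording stops at deflation. The overlap with the numerator window is 0 of 60 seconds.
2. Recording stops at some later, unstated time. If that is 2 minutes or more after deflation, the overlap is 60 of 60 seconds.

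The wording does not force reading 1. It gives a sequence, deflate and then stop, without saying that the second step is immediate. Three places rule reading 1 out:

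- The sentence itself gives the production of hyperaemia as the reason for deflating.
- Section 2.2 says that the method measures pulse volume during hyperaemia as well as at rest, and its figure caption refers to responses both before and after occlusion.
- Section 7.2.4, which follows directly, sets a window that exists only if recording continues.

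**Does the missing duration affect the result under reading 2?** Both windows are fixed relative to inflation and deflation, and Section 7.2.4 says that the computer analysis does not depend on the operator. A stop at 2, 3 or 5 minutes after deflation gives the same numerator, denominator and index. Stop times that differ between subjects or diet phases therefore add neither bias nor variance, provided that each is at least 2 minutes.

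**The case for a change.** The strongest case for a change is that a procedure should be usable on its own. Section 7.2.4 is headed as analysis and written partly in the past tense, and staff running the session may not consult it. The sentence is ungrammatical, as though a clause had dropped out, so what remains is a broken instruction for the primary endpoint. A repair would take one sentence, and the 2 minutes would come from the protocol's own definition.

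Part of this stands. The omission is real, the 2-minute minimum is correct, and stating it in Section 7.2.3 would be tidier drafting. The times given for ultrasound and calf blood flow belong to other instruments and cannot be borrowed for PAT.

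What does not stand is the step from an unstated duration to a risk for the endpoint. An unspecified stop time does not contradict a specified window; the conflict appears only under the zero-interval reading, which nobody argues was intended. Nothing in the document says that staff work from Section 7.2.3 without Section 7.2.4, and stopping before the hyperaemic response would defeat the purpose of the test. The comparison with ultrasound is also weaker than it looks. That procedure has no separate section fixing a window after deflation, so its duration has to appear in the procedure, whereas for PAT the next section supplies the minimum.

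**Conclusion.** The concern does not call for a change. Section 7.2.3 leaves out how long recording continues after deflation, and Section 7.2.4 supplies the answer: at least 2 minutes on both hands, to minute 17 from the start of equilibration. Staff who read the two adjacent sections together will record through the window and obtain the index as defined. Adding the duration would write down what the plan already implies. The endpoint definition, the signed-rank test, the sample size of 44 and its 90% power would all stay as they are.

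This rests on two assumptions: that operators know the index window when they run the session, and that recordings at both diet visits reach at least 2 minutes after deflation. The document gives no reason to doubt either. The figure of 0 of 60 seconds describes the harshest reading of one sentence and is not an estimate of lost data. If the sponsor revises the text for other reasons, the sentence can be tidied as an editorial matter.
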